8.4.5.2. Exposure During Breastfeeding

An EDB occurs if:

- A female participant is found to be breastfeeding while receiving or after discontinuing study intervention.
- A female nonparticipant is found to be breastfeeding while being exposed or having been exposed to study intervention (ie, environmental exposure). An example of environmental EDB is a female family member or healthcare provider who reports that she is breastfeeding after having been exposed to the study intervention by ingestion.

The investigator must report EDB to Pfizer Safety within 24 hours of the investigator's awareness, irrespective of whether an SAE has occurred. The information must be reported using the CT SAE Report Form. When EDB occurs in the setting of environmental exposure, the exposure information does not pertain to the participant enrolled in the study, so the information is not recorded on a CRF. However, a copy of the completed CT SAE Report Form is maintained in the investigator site file.

An EDB report is not created when a Pfizer drug specifically approved for use in breastfeeding women (eg, vitamins) is administered in accordance with authorized use. However, if the infant experiences an SAE associated with such a drug, the SAE is reported together with the EDB.

8.4.5.3. Occupational Exposure

The investigator must report any instance of occupational exposure to Pfizer Safety within 24 hours of the investigator's awareness using the CT SAE Report Form regardless of whether there is an associated SAE. Since the information about the occupational exposure does not pertain to a participant enrolled in the study, the information is not recorded on a CRF; however, a copy of the completed CT SAE Report Form must be maintained in the investigator site file.

8.4.6. Cardiovascular and Death Events

Not applicable.

8.4.7. Disease-Related Events and/or Disease-Related Outcomes Not Qualifying as AEs or SAEs

Not applicable.

8.4.8. Adverse Events of Special Interest

Not applicable.

8.4.8.1. Lack of Efficacy

This section is not applicable because efficacy is not expected in the study population.

8.4.9. Medical Device Deficiencies

Not applicable.

8.4.10. Medication Errors

Medication errors may result from the administration or consumption of the study intervention by the wrong participant, or at the wrong time, or at the wrong dosage strength.

Medication errors are recorded and reported as follows:

Recorded on the Medication Error Page of the CRF	Recorded on the Adverse Event Page of the CRF	Reported on the CT SAE Report Form to Pfizer Safety Within 24 Hours of Awareness
All (regardless of whether associated with an AE)	Any AE or SAE associated with the medication error	Only if associated with an SAE

Medication errors include:

- Medication errors involving participant exposure to the study intervention;
- Potential medication errors or uses outside of what is foreseen in the protocol that do or do not involve the study participant.

Such medication errors occurring to a study participant are to be captured on the medication error page of the CRF, which is a specific version of the AE page.

Whether or not the medication error is accompanied by an AE, as determined by the investigator, the medication error is recorded on the medication error page of the CRF and, if applicable, any associated AE(s), serious and nonserious, are recorded on the AE page of the CRF.

In the event of a medication dosing error, the sponsor should be notified within 24 hours.

Medication errors should be reported to Pfizer Safety within 24 hours on a CT SAE Report Form **only when associated with an SAE.**

8.5. Pharmacokinetics

8.5.1. Plasma for Analysis of PF-07081532

Blood samples of approximately 3 mL, to provide a minimum volume of 1 mL plasma, will be collected into appropriately labeled tubes containing K₂EDTA for measurement of plasma concentrations of PF-07081532 as specified in the SoA. Instructions for the collection and handling of biological samples will be provided in the laboratory manual or by the sponsor. The actual date and time (24-hour clock time) of each sample will be recorded.

The actual times may change, but the number of samples will remain the same. All efforts will be made to obtain the samples at the exact nominal time relative to dosing. Collection of samples up to and including 10 hours after dose administration that are obtained within 10% of the nominal time relative to dosing (eg, within 6 minutes of a 60-minute sample) will not be captured as a protocol deviation, as long as the exact time of the collection is noted on the source document and the CRF. Collection of samples more than 10 hours after dose administration that are obtained ≤1 hour away from the nominal time relative to dosing will not be captured as a protocol deviation, as long as the exact time of the collection is noted on the source document and the CRF.

Samples will be used to evaluate the PK of PF-07081532. Samples collected for analyses of plasma concentration may also be used to evaluate safety or efficacy aspects related to concerns arising during or after the study, for metabolite identification and/or evaluation of the bioanalytical method, or for other internal exploratory purposes.

Genetic analyses will not be performed on these plasma samples unless consent for this was included in the informed consent. Participant confidentiality will be maintained.

Samples collected for measurement of plasma concentrations of PF-07081532 will be analyzed using a validated analytical method in compliance with applicable SOPs. Potential metabolites may be analyzed with either validated or exploratory methods.

The PK samples must be processed and shipped as indicated in the instructions provided to the investigator site to maintain sample integrity. Any deviations from the PK sample handling procedure (eg, sample collection and processing steps, interim storage or shipping conditions), including any actions taken, must be documented and reported to the sponsor. On a case-by-case basis, the sponsor may make a determination as to whether sample integrity has been compromised.

8.5.2. Plasma for Determination of PF-07081532 Unbound Fraction

During the study, blood samples of approximately 10 mL to provide sufficient plasma (approximately 4 mL) for unbound fraction determination, will be collected into appropriately labeled tubes containing K₂EDTA, as specified in the SoA. Instructions for the collection and handling of biological samples will be provided in the laboratory manual or by the sponsor. The actual date and time (24-hour clock time) of each sample will be recorded.

The actual times may change, but the number of samples will remain the same. All efforts will be made to obtain the samples at the exact nominal time relative to dosing. Collection of samples up to and including 10 hours after dose administration that are obtained within 10% of the nominal time relative to dosing (eg, within 6 minutes of a 60-minute sample) will not be captured as a protocol deviation, as long as the exact time of the collection is noted on the source document and the CRF.

Samples collected for analyses of PF-07081532 plasma protein binding may also be used to evaluate safety or efficacy aspects related to concerns arising during or after the study, for metabolite identification and/or evaluation of the bioanalytical method, or for other internal exploratory purposes.

Genetic analyses will not be performed on these plasma samples unless consent for this was included in the informed consent. Participant confidentiality will be maintained.

Samples collected for measurement of PF-07081532 plasma protein binding will be analyzed using a validated analytical method in compliance with applicable SOPs. Potential metabolites may be analyzed with either validated or exploratory methods.

The samples for determination of PF-07081532 plasma protein binding must be processed and shipped as indicated in the instructions provided to the investigator site to maintain sample integrity. Any deviations from the sample handling procedure (eg, sample collection and processing steps, interim storage or shipping conditions), including any actions taken, must be documented and reported to the sponsor. On a case-by-case basis, the sponsor may make a determination as to whether sample integrity has been compromised.

8.5.3. Urine for Analysis of PF-07081532

Urine will be collected at times specified in the SoA (NOTE that no urine will be collected for anuric dialysis participants).

- **Prior to dosing** on Day 1, each participant must complete a forced void with an aliquot (approximately 10 mL) from this urine (urine blank), labeled and stored frozen for measurement of drug concentrations, per detailed instructions offered in a laboratory manual prior to the start of the study.
- Following dosing on Day 1, each void post dose will be collected and saved in a container and stored in refrigerated conditions (ie, 2-8°C) for the duration of the collection interval, as specified in the SoA.
 - At the end of each collection interval, participants must complete a forced void with this complete void included as part of the interval collection. Each collection interval should have its own collection container.

 At the end of each urine collection interval, all urine collected in the associated collection container will be mixed thoroughly and total volume plus weight of the urine collected during the interval will be recorded. Subsequently, a urine aliquot (approximately 2 mL) will be withdrawn for measurement of PF-07081532 concentrations.

Details regarding the processing, storage and shipping of the samples will be provided in the laboratory manual. Samples collected for urine analyses of PF-07081532 may also be used to evaluate safety or efficacy aspects related to concerns arising during or after the study, for metabolite identification and/or evaluation of the bioanalytical method, or for other internal exploratory purposes. The shipment address and assay lab contact information will be provided to the investigator site prior to initiation of the study. The urine samples must be processed as indicated to maintain sample integrity. Any deviations from the urine sample processing steps given in the protocol or lab manual, including any actions taken, must be documented and reported to the sponsor. On a case by case basis, the sponsor may make a determination as to whether sample integrity has been compromised. Any sample deemed outside of established stability, or of questionable integrity, will be considered a protocol deviation. Samples for urine PK analysis of PF-07081532 will be analyzed using validated analytical methods in compliance with Pfizer SOPs.

8.6. Genetics

8.6.1. Specified Genetics

Specified genetic analyses are not evaluated in this study.

8.6.2. Retained Research Samples for Genetics

A 2 mL blood sample optimized for DNA isolation Prep D1.5 will be collected according to the SoA, as local regulations and IRBs/ECs allow.

Retained Research Samples may be used for research related to the study intervention(s) and reanl impairment. Genes and other analytes (eg, proteins, RNA, nondrug metabolites) may be studied using the retained samples.

See Appendix 5 for information regarding genetic research. Details on processes for collection and shipment of these samples can be found in the lab manual.

8.7.2. Specified Gene Expression (RNA) Research

Specified gene expression (RNA) research is not included in this study.

8.7.3. Specified Protein Research

Specified protein research is not included in this study.

8.7.4. Specified Metabolomic Research

Specified metabolomic research is not included in this study.

8.8. Immunogenicity Assessments

Immunogenicity assessments are not included in this study.

8.9. Health Economics

Health economics/medical resource utilization and health economics parameters are not evaluated in this study.

9. STATISTICAL CONSIDERATIONS

Detailed methodology for summary and statistical analyses of the data collected in this study is outlined here and further detailed in the SAP, which will be maintained by the sponsor. The SAP may modify what is outlined in the protocol where appropriate; however, any major modifications of the primary endpoint definitions or their analyses will also be reflected in a protocol amendment.

9.1. Statistical Hypotheses

No formal statistical hypothesis testing will be performed in this study.

9.2. Analysis Sets

For purposes of analysis, the following analysis sets are defined:

Participant Analysis Set	Description
Enrolled	"Enrolled" means a participant's, or their legally authorized representative's, agreement to participate in a clinical study following completion of the informed consent process and assignment to study intervention. A participant will be considered enrolled if the informed consent is not withdrawn prior to participating in any study activity after screening. Potential participants who are screened for the purpose of determining eligibility for the study, but do not participate in the study, are not considered enrolled, unless otherwise specified by the protocol.

Participant Analysis Set	Description	
Safety analysis set	All participants assigned to study intervention and who take at least 1 dose of study intervention.	
PK Concentration Set	The PK concentration population is defined as all participants who received at least 1 dose of PF-07081532 and in whom at least 1 plasma concentration value is reported.	
PK Parameter Set	The PK parameter analysis population is defined as all participants who received at least 1 dose of PF-07081532 and have at least 1 of the PK parameters of interest calculated.	

9.3. Statistical Analyses

The SAP will be developed and finalized before any analyses are performed and will describe the analyses and procedures for accounting for missing, unused, and spurious data. This section is a summary of the planned statistical analyses of the primary and secondary endpoints.

9.3.1. General Considerations

Endpoints will be reported and analyzed according to the renal impairment group to which participants actually belong, based on their average eGFR value (see Table 1).

9.3.1.1. Analyses for PK Endpoints

Natural log-transformed PK parameters will be analyzed using an ANOVA model including renal impairment group as fixed effect. Estimates of the adjusted means and of the adjusted mean differences (Test-Reference) with their corresponding 90% CIs will be obtained before being exponentiated to provide estimates of the adjusted geometric means and of the ratio of adjusted geometric means (Test/Reference).

9.3.2. Primary Endpoint(s) Analysis

9.3.2.1. Definition of Endpoint(s)

The plasma PK parameters for PF-07081532 following single dose administration will be derived from the concentration-time profiles as detailed in Table 2. Actual PK sampling times will be used in the derivation of plasma PK parameters. In the case that actual PK sampling times are not available, nominal PK sampling time will be used in the derivation of plasma PK parameters. The fraction of PF-07081532 unbound in plasma (f_u) will be determined by the analytical lab and reported for each participant.

The urine PK parameters listed in Table 3 will be calculated for PF-07081532.

 Table 2.
 Plasma PK Parameters

Parameter	Definition	Method of Determination
AUC _{last}	Area under the plasma concentration- time profile from time zero to the time of the last quantifiable concentration (C_{last}).	Linear/Log trapezoidal method.
AUC _{inf} *	Area under the plasma concentration- time profile from time zero extrapolated to infinite time.	AUC _{last} + (C _{last} */k _{el}), where C _{last} * is the predicted plasma concentration at the last quantifiable time point estimated from the log-linear regression analysis.
C _{max}	Maximum plasma concentration.	Observed directly from data.
T_{max}	Time for C _{max} .	Observed directly from data as time of first occurrence.
t _{1/2} *	Terminal half-life.	Log _e (2)/k _{el} , where k _{el} is the terminal phase rate constant calculated by a linear regression of the log-linear Concentration-time curve. Only those data points judged to describe the terminal log-linear decline will be used in the regression.
CL/F*	Apparent clearance.	Dose/AUC _{inf} .
V _z /F*	Apparent volume of distribution.	Dose/(AUC _{inf} ·k _{el}).
fu	Fraction of unbound drug in plasma.	Cu/C (where Cu represents unbound concentration and C represents total concentration).
AUC _{last,u}	Unbound AUC _{last} .	fu·AUC _{last} .
AUC _{inf,u} *	Unbound AUC _{inf} .	fu·AUC _{inf} .
C _{max,u}	Unbound C _{max} .	fu·C _{max} .
CL _u /F*	Unbound CL/F.	Dose/AUC _{inf,u} .
V _{z,u} /F*	Unbound V _z /F.	Dose/(AUC _{inf,u} ·k _{el}).

^{*} as data permit.

Table 3. Urine PK Parameters

Parameter	Definition	Method of Determination
Ae ₂₄	Total amount of unchanged drug excreted in urine over 24 hours.	Sum of amount excreted for each collection period.
Ae ₂₄ %	Total amount of unchanged drug excreted in urine over 24 hours, expressed as percent of dose.	100·(Ae ₂₄ /Dose)
CL_r	Renal clearance.	Ae ₂₄ /AUC ₂₄ .

9.3.2.2. Main Analytical Approach

The effect of varying degrees of renal impairment on PK parameters will be assessed by constructing 90% CIs around the estimated difference between each of the Test (renal impaired) groups and the Reference (without renal impairment) group. A one-way ANOVA will be used to compare the natural log transformed PF-07081532 AUC_{inf}, C_{max}, AUC_{last}, f_u, and associated unbound parameters (AUC_{inf,u}, C_{max,u}, AUC_{last,u}), as data permit, for each of the renal impairment groups (Test) to the group without renal impairment (Reference). Estimates of the adjusted mean differences (Test - Reference), and corresponding 90% CIs, will be obtained from the model. These will be exponentiated to provide estimates of the ratio of adjusted geometric means (Test/Reference) and 90% CIs for the ratios.

Individual PF-07081532 concentrations will be listed and summarized descriptively by nominal PK sampling time and renal impairment group. Individual participant and summary profiles of the concentration-time data (using actual and nominal times, respectively) will be plotted by renal impairment group for both total plasma PF-07081532 and unbound PF-07081532.

Box and whisker plots for individual PK parameters (AUC_{inf}, AUC_{last}, C_{max}, f_u, AUC_{inf,u}, AUC_{last,u} and C_{max,u}) will be constructed by renal impairment group and overlaid with geometric means. PK parameters of PF-07081532 will be listed and summarized descriptively by renal impairment group

For summary statistics and median or mean plots by sampling time, the nominal PK sampling time will be used. For individual partivipant plots by time, the actual PK sampling time will be used.

9.3.2.3. Supplementary Analyses

Linear regression may be used to characterize the potential relationship between appropriate PK parameters (eg, CL/F, CL_u/F and CL_r) for PF-07081532 and renal function (eGFR). eGFR values obtained on Day 1 will be included in the regression analysis. Estimates of the statistical slope and intercept, together with their precision (90% CIs), and the coefficient of determination will be obtained from the model.

The effect of covariates such as weight, gender, and age may be explored, and details will be provided in the SAP.

Plots of PK parameters (eg, CL/F, CL_u/F and CL_r) for PF-07081532 versus renal function (eGFR as obtained on Day 1) will be constructed. A regression line and 90% confidence region for the PK parameters and eGFR will be included if appropriate. Vertical lines for the renal function group cut-off values will also be presented on the plots. Different symbols will be used to identify participants from different renal function groups.

Exploratory analyses, similar to those listed above (using the eGFR values determined with the 2021 CKD-EPI Scr-Scys combined equation) may be conducted using eGFR values determined with the 2021 CKD-EPI Scr only, the Cockcroft-Gault or the MDRD formulas as described in the SAP.

9.3.3. Secondary Endpoint Analysis - Safety Analyses

All safety analyses will be performed on the safety population.

AEs, ECGs, BP, pulse rate, and safety laboratory data will be reviewed and summarized on an ongoing basis during the study to evaluate the safety of participants. Any clinical laboratory, ECG, BP, and pulse rate abnormalities of potential clinical concern will be described. Safety data will be presented in tabular and/or graphical format and summarized descriptively, where appropriate following sponsor standards.

Medical history and physical examination collected during the course of the study, will be considered source data and will not be required to be reported, unless otherwise noted. However, any untoward findings identified on physical examinations conducted during the active collection period will be captured as AEs, if those findings meet the definition of an AE. Data collected at screening that are used for inclusion/exclusion criteria, such as laboratory data, ECGs, and vital signs, will be considered source data, and will not be required to be reported, unless otherwise noted. Demographic data collected at screening will be reported. Alcohol test results will be considered source data and will not be required to be reported. COVID-19 specific assessment data will remain as source and will not be reported.

9.3.3.1. Electrocardiogram Analyses

Changes from baseline for the ECG parameters HR, QTcF, PR interval, and QRS complex will be summarized by treatment and time. The frequency of uncorrected QT values above 500 ms will be tabulated.

The number (%) of participants with maximum post-dose QTcF values and maximum increases from baseline in the following categories will be tabulated by treatment:

Safety QTcF Assessment

Degree of Prolongation	Mild (ms)	Moderate (ms)	Severe (ms)
Absolute value	>450-480	>480-500	>500
Increase from baseline		30-60	>60

9.3.5. Other Analyses

Pharmacogenomic or biomarker data from Retained Research Samples may be collected during or after the trial and retained for future analyses; the results of such analyses are not planned to be included in the CSR.

9.4. Interim Analyses

No formal interim analysis will be conducted for this study. As this is an open-label study, the sponsor may conduct unblinded reviews of the data during the course of the study for the purpose of safety assessment, facilitating PK modeling, and/or supporting clinical development.

9.5. Sample Size Determination

A sample size of approximately 32 participants (approximately 8 participants per group, with varying degrees of renal function in each of the 4 groups) has been selected to provide sufficient precision to detect at least a 1.5-fold difference in AUC_{inf} between each Test group (with renal impairment) and the Reference group (without renal impairment). Table 4 presents the 90% CIs (with 80% coverage probability) for various possible effects on AUC_{inf}. The same table would be applicable for possible effects on C_{max}.

Table 4. Expected Widths of the 90% CIs (with 80% Coverage Probability) for Different Possible Estimated Effects

Estimated Effect	AUCinf	
(Test/Reference)	Probable 90% CI	Probable CI Width
75%	52% to 109%	58%
100%	69% to 146%	77%
150%	103% to 218%	115%
200%	137% to 291%	154%
400%	275% to 582%	307%

These estimates are based on an assumed conservative standard deviation of 0.4 for log_eAUC_{inf} (also applicable to log_eC_{max}) based on data from previous internal studies with PF-07081532 administered either as a single dose in the fed/fasted state in healthy participants (C3991001) or as multiple doses in the fed state in participants with T2DM (C3991002).

Participants who discontinue from the study before completing all assessments may be replaced at the discretion of the investigator and sponsor.

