- At Screening (S1), seated SBP ≥160 mmHg and/or DBP ≥100 mmHg after ≥5 minutes of seated rest. If BP is ≥160 mm Hg (systolic) or ≥100 mm Hg (diastolic), the BP should be repeated 2 more times and the average of the 3 BP values should be used to determine the participant's eligibility
- In addition, for participants with impaired renal function:
 - Any of the following abnormalities in clinical laboratory tests at Screening, as assessed by the sponsor-identified laboratory and confirmed by a single repeat test, if deemed necessary:
 - AST $\geq 2x$ ULN or
 - ALT ≥2x ULN
 - At Screening, Day -1 or Day 1, persistent severe, uncontrolled hypertension, as defined in the study protocol.

Study Arms and Duration:

Eligible participants with T2DM will be enrolled into 1 of 4 groups based on eGFR (calculated using the **2021** CKD-EPI Scr-Scys combined equation):

- 1. Normal renal function (≥90 mL/min).
- 2. Mild (60-89 mL/min) renal impairment.
- 3. Moderate (30-59 mL/min) renal impairment.
- 4. Severe (<30 mL/min) renal impairment.

A single oral 20 mg dose of PF-07081532 will be administered. For individual participants, the total study duration from Screening visit S1 to the Follow-up contact will be a minimum of approximately 6 weeks and a maximum of up to approximately 10 weeks. The study consists of an initial screening period of up to 28 days, a 7-day inpatient stay at the CRU which includes administration of a single oral dose of PF-07081532, and a follow up contact that will occur 28-35 days after PF-07081532 administration.

PF-07081532 will be supplied by Pfizer as 20 mg tablets in open-label bulk bottles along with individual dosing containers, as necessary, for unit dosing. Participants will take 1 PF-07081532 20-mg tablet orally with the morning meal.

Study Intervention(s)	
Intervention Name	PF-07081532
Arm Name (group of participants receiving a specific treatment or no treatment)	Group 1, Group 2, Group 3, Group 4
Unit Dose Strength(s)	20 mg
Route of Administration	Oral
Use	Experimental
IMP or NIMP/AxMP	IMP

Statistical Methods:

A sample size of approximately 32 participants (approximately 8 participants per group, with varying degrees of renal function in each of the 4 groups) has been selected to provide sufficient precision to detect a 1.5-fold difference in AUC_{inf} between each Test group (with renal impairment) and the Reference group (without renal impairment).

[figure not shown]

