4. STUDY DESIGN

4.1. Overall Design

This is an open-label, single-dose, parallel-group study to investigate the effect of varying degrees of renal function on the PK of PF-07081532 after a single, oral 20 mg dose administered in the fed state (standard, non-high fat breakfast). Safety and tolerability will be evaluated throughout the study.

A total of approximately 32 participants with T2DM and varying degrees of renal function will be dosed in the study as shown in Table 1. If recruitment of participants with eGFR <30 mL/min proves prohibitive, the number of participants to be enrolled in the group with severe impairment may be flexible (6-8 participants). This study will permit enrollment of 2-4 participants on dialysis, as part of the severe renal impairment group, to assist in recruitment of patients with more advanced renal impairment and to permit assessment of the PK of PF-07081532 in participants with the highest degree of renal impairment. Since PF-07081532 has a high unbound non-renal clearance and a large unbound volume of distribution (given a fu of 0.000376 in humans), dialysis is not expected to significantly impact the clearance of PF-07081532 and therefore the dialysis clearance of PF-07081532 will not be characterized in this study. Thus, Day 1 (per the SoA) will occur in dialysis patients on a day in which dialysis is not administered.

Table 1. Renal Function Categories based on eGl	Table 1.	Renal	Function	Categories	based	on eGF
---	----------	-------	----------	------------	-------	--------

Group	Renal Impairment	No. of Participants	eGFR ^a
			(mL/min)
1	None (Normal Renal Function)	8	≥90
2	Mild	8	60-89
3	Moderate	8	30-59
4	Severe	8 ^b	< 30

- a. See text below regarding determination of eGFR for study enrollment and group placement.

 Note: participants on dialysis will be placed in Group 4 regardless of unnormalized eGFR value.
- b. 2-4 participants on dialysis are permitted (not required). If recruitment proves to be prohibitive, study may dose 6-8 participants with severe renal impairment.

Screening will occur within 28 days of the first dose of study intervention on Day 1. All participants will provide informed consent and undergo Screening evaluations to determine their eligibility.

At each of the 2 Screening visits (S1 and S2), an estimate of eGFR will be determined for each participant as described in the steps below:

- 1. Calculate eGFR using the **2021** CKD-EPI Scr-Scys combined equation (see Appendix 7).

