2.3. Study Design

This is an open-label, single-dose, parallel-group study to investigate the effect of varying degrees of renal function on the PK of PF-07081532 after a single, oral 20 mg dose administered in the fed state (standard, non-high fat breakfast). Safety and tolerability will be evaluated throughout the study. A total of approximately 32 participants with T2DM and varying degrees of renal function will be dosed in the study as shown in Table 2. If recruitment of participants with eGFR <30 mL/min proves prohibitive, the number of participants to be enrolled in the group with severe impairment may be flexible (6-8 participants).

Table 2. Renal Function Categories Based on eGFR
--

Group	Renal Impairment	eGFR ^a (mL/min) ^a	Number of Participants
1	None (Normal Renal Function)	≥90	8
2	Mild	60-89	8
3	Moderate	30-59	8
4	Severe	<30	8^b

a. Note:participants on dialysis will be placed in Group 4 regardless of unnormalized eGFR value.

Categorization of participants into Groups 2-4 will be done based on eGFR values determined at the screening visit, as described in Section 4.1 of the protocol.

b. 2-4 participants on dialysis are permitted (not required). If requirement proves to be prohibitive, study may dose 6-8 participants with severe renal impairment.

Staged Enrollment of Study Groups

- Participants will be dosed in a staged manner such that those with moderate and severe renal impairment (Groups 3 and 4) will be enrolled first.
- Recruitment of participants with mild renal impairment (Group 2) will initiate when approximately 50% of the participants in Groups 3 and 4 have been dosed.

Approval from the sponsor is required before proceeding with recruitment of Group 2.

- An average value for age and weight for Groups 2, 3, and 4 will be determined and participants in Group 1 will be recruited to match the average demographics (at a minimum, age and weight, and as much as practically possible gender) across the pooled Groups 2-4.
- Therefore, recruitment of participants without renal impairment (Group 1) may start when approximately 75% of total participants across Groups 2-4 (ie, approximately 17-18 participants) have been dosed.

Approval from the sponsor is required before proceeding with recruitment of Group 1.

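### Does Table 4 fail to support the claim that 8 per group is precise enough for a 1.5-fold difference in AUCinf, given that the severe group may have only 6?

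*Protocol*

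**What the plan says.** Protocol Section 9.5 states that the sample size, "approximately 8 participants per group" in four groups, "has been selected to provide sufficient precision to detect at least a 1.5-fold difference in" AUCinf between each Test group and the Reference group. The Synopsis uses nearly the same words: "sufficient precision to detect a 1.5-fold difference in" AUCinf.

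The support is Table 4, headed "Expected Widths of the 90% CIs (with 80% Coverage Probability) for Different Possible Estimated Effects". Its row for an estimated effect of 150% reads 103% to 218%, width 115%. The table rests on an "assumed conservative standard deviation of 0.4" for log AUCinf, which Section 9.5 also applies to log Cmax.

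Protocol Section 9.1 says: "No formal statistical hypothesis testing will be performed in this study". SAP Section 5.1 agrees and adds that there are no decision rules. Protocol Section 9.3.2.2 says that the effect of renal impairment will be assessed with 90% confidence intervals for each Test/Reference comparison, and the Synopsis specifies one ANOVA containing all groups.

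The severe group may be smaller than planned if recruitment is too difficult. Protocol Section 4.1 allows for this, and footnote b to Table 2 in SAP Section 2.3 says that the "study may dose 6-8 participants with severe renal impairment". Table 4 has no rows for a group of fewer than 8.

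**The concern.** Section 9.5 is the only justification for the group size. Two features of it look unsound.

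- **Observed against true ratio.** To *detect* a difference normally means that a true difference of that size would be seen with a stated, high probability. Table 4 is conditional on the ratio that happens to be estimated and gives no such probability. A reader could conclude that a true 1.5-fold rise in exposure would usually produce an interval above 100%.
- **The smaller severe group.** The claim is made for each Test group, but the protocol permits 6 in the severe group, and precision at that size is not shown. If the 150% row failed to clear 100% there, the claim would fail in the group with the most advanced impairment.

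At stake is whether the design gives the precision that it advertises. The results are meant to feed into dosing recommendations.

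**Working it through.** **Inputs.** SD 0.4 on the log scale; 8 per group, or 6 to 8 in the severe group; two-sided 90% intervals; 80% probability that the interval is no wider than shown (Protocol Sections 9.5 and 4.1). One ANOVA with four groups (Synopsis), so the residual degrees of freedom are 32 − 4 = 28, or 30 − 4 = 26 with 6 severe participants.

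**Step 1: reproduce Table 4.** The log half-width is

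h = t(0.95, df) × SD × √(1/n₄ + 1/8) × √(χ²(0.80, df)/df).

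For n₄ = 8 and df = 28: h = 1.7011 × 0.4 × √(1/8 + 1/8) × √(34.03/28) = 1.7011 × 0.2000 × 1.1024 = 0.3751. The limits are the ratio times exp(±0.3751), that is, divided or multiplied by 1.455.

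| Estimated ratio | Recomputed | Table 4 |
|---|---|---|
| 75% | 51.5 to 109.1, width 57.6 | 52 to 109, 58 |
| 100% | 68.7 to 145.5, width 76.8 | 69 to 146, 77 |
| 150% | 103.1 to 218.3, width 115.2 | 103 to 218, 115 |
| 200% | 137.5 to 291.0, width 153.6 | 137 to 291, 154 |
| 400% | 274.9 to 582.0, width 307.1 | 275 to 582, 307 |

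Every entry matches. Two-group degrees of freedom (14) would give 100 to 224 in the 150% row, so the table was built on the model that will be fitted.

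**Step 2: the sentence as a precision statement.** If the observed ratio is 1.5, the tabulated lower limit is 103%, so the interval lies above 100%. The smallest observed ratio with that property is exp(0.3751) = 1.46. Given an observed 1.5 and a true SD of 0.4, the probability that the lower limit exceeds 100% is P(χ²₂₈ ≤ 28 × [ln 1.5 / (1.7011 × 0.2)]²) = P(χ²₂₈ ≤ 39.77) = 93%.

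**Step 3: a smaller severe group.**

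| Severe n | df | h | 150% row | 100% row |
|---|---|---|---|---|
| 8 | 28 | 0.3751 | 103.1 to 218.3 | 68.7 to 145.5 |
| 7 | 27 | 0.3893 | 101.6 to 221.4 | 67.8 to 147.6 |
| 6 | 26 | 0.4075 | 99.8 to 225.4 | 66.5 to 150.3 |

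At n = 6, h = 1.7056 × 0.2160 × √(31.79/26) = 0.4075. The lower limit of 99.8% prints as 100% at the table's rounding. Given an observed 1.5, the probability that the interval lies above 100% is P(χ²₂₆ ≤ 31.49) = 78.9%, against the 80% on which the table is built. The shortfall vanishes at n = 7, or at an SD of 0.398.

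**Step 4: the power reading.** Assume that *detect* means a lower 90% limit above 100% when the true ratio is 1.5. The noncentrality is ln 1.5 / SE: 0.4055/0.2000 = 2.027 for n = 8, and 0.4055/0.2160 = 1.877 for n = 6. The noncentral t gives the following probabilities.

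| True SD | n = 8 | n = 6 |
|---|---|---|
| 0.40 | 63% | 57% |
| 0.35 | 73% | 67% |
| 0.30 | 84% | 79% |

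At SD 0.4, an 80% probability would need a true ratio of 1.66 (n = 8) or 1.74 (n = 6). At a true ratio of 1.5 it would need an SD of about 0.32 or less (n = 8), or 13 per group at SD 0.4.

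**The case for a change.** The strongest case for a change is that *detect a difference* ordinarily refers to a true difference. On that reading the design succeeds in only 63% of trials at its own SD, and for a severe group of 6 the sentence narrowly fails even on the favourable reading. The Synopsis makes the claim in its text without Table 4 beside it. The documents give no observed SD against which to judge whether 0.4 is conservative. The remedy would also be cheap: a few words in two places and one more block of rows.

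Some of this stands. *Detect* is loose, no probability is given for a true 1.5-fold change, and the smaller group is not tabulated. But both sentences speak of precision, and the table says that it is conditional on the estimated effect. No power figure is stated that the design could miss. The 63% and 57% describe a test that both documents say will not be done. The smaller severe group is a fallback, available only if recruitment proves too difficult, and it misses by 0.2 percentage points on the lower limit. Tabulating the planned size is normal practice.

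**Conclusion.** The concern does not call for a change. Table 4 is correct for 8 per group. Read as the documents frame it, as precision around an observed ratio, its 150% row (lower limit 103%) supports the sentence. The severe group of 6 costs little: the 150% row becomes 100% to 225% at the table's rounding, with 78.9% instead of 80% assurance.

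A reader who wants the probability for a true 1.5-fold difference should use about 63% (8 per group) or 57% (6 severe participants). These figures assume SD 0.4, the pooled four-group model, and *detect* meaning a lower 90% limit above 100%; that definition is not in the documents. With a smaller SD the probabilities are higher.

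Rewording the sentence and adding rows for 6 against 8 would be a reasonable editorial courtesy if the protocol were amended for another reason. It would alter no enrolment target, model or reported interval, because the intervals in the study report will be calculated from the data and the group sizes achieved.
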